
f. Only guselkumab clinical responders at Week I 12 and placebo crossover responders at Week I 24 will be rerandomized in the Maintenance Study. Guselkumab 24 Week responders and induction placebo responders at Week I 12 will enter the Maintenance study but will not be rerandomized.
 
g. All assessments are to be completed before study intervention administration, unless otherwise specified. It is recommended that PRO assessments be completed first.
 
h. For all assessments not marked at this visit, data from the study assessments performed at the Week I 12 visit (for participants in clinical response at Week I 12) or at the Week I 24 visit (for participants who were not in clinical response at Week I 12 but were in clinical response at Week I 24) will be used for the Week M 0 visit.
 
i. A participant who meets the criteria for clinical flare for the first time prior to Week M 32 should undergo an endoscopy (which need only be a flexible sigmoidoscopy) to determine loss of clinical response based on the modified Mayo score (Section 4.1.3.1).
 
j. If TB is suspected at any time during the study, a chest radiograph and QuantiFERON TB[®] (or T SPOT[®] for sites in Japan) test should be performed. In countries/territories where the QuantiFERON TB[®] test is not registered/approved, TB skin testing should also be performed (recommended but not required for study centers in Ukraine if tuberculin is not available).
 
k. Temperature, pulse/heart rate, respiratory rate, and blood pressure. At a study intervention administration visit, vital signs should be obtained before and approximately 30 minutes after SC injection, or if the participant reports any symptoms.
 
l. A urine pregnancy test must be performed before any study intervention administration for women of childbearing potential.
 
m. The C SSRS should be completed after all PROs and before any other tests, procedures, or other consultations to prevent influencing participant perceptions.
 
n. An injection site reaction is any adverse reaction at any SC study intervention injection site. Injection sites will be evaluated for reactions and any injection site reaction should be recorded as an adverse event.
 
o. Predose samples should be collected at all dosing visits before study intervention administration. All reasonable attempts should be made to collect samples at the scheduled time points and record the actual dates and times of sample collections.
 
p. Colonic biopsy samples will be collected from all participants during endoscopy for histologic assessment and RNA transcriptomic analysis. Pre defined sites will collect adjacent biopsy samples to support exploratory single cell isolation and analyses.
 
q. Whole blood samples will be collected for PBMC isolation from a subset of participants that provide biopsy samples for single cell analyses at selected sites. Whole blood (PBMC) samples should be collected within ±3 days of the endoscopy visit.
 
r. Serum biomarkers will be measured in all participants to evaluate the effects of study intervention on inflammatory proteins associated with UC, including cytokines associated with the IL 23 pathway.
 
s. Whole blood (RNA) will be measured in all participants to evaluate the molecular effects of study intervention in UC.
 
t. Fecal biomarkers may be used for evaluation of changes in inflammatory proteins or microbiome composition.
 
u. Participants who complete the safety and efficacy evaluations (including the required endoscopy procedure) at maintenance Week M 44 and who may benefit from continued study intervention, in the opinion of the investigator, will have the opportunity to participate in the LTE of the Maintenance Study.
 
v. At visits also requiring endoscopy, stool samples should be collected prior to the initiation of endoscopy bowel preparations. Refer to the At Home Stool Collection Manual for detailed instructions.
 
w. Should be completed if the Week M 0 visit is completed on a day other than that of the Week I 12 visit or Week I 24 visit.
 
x. Corticosteroid tapering must begin at M 0 for all participants receiving corticosteroids at baseline. Refer to Section 6.5.1 for guidance and requirements for corticosteroid use.
														

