5.1.4. Maintenance Baseline Definition

The maintenance baseline is defined as the closest non-missing value on or prior to the maintenance reference start date which is also post-induction baseline.

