- Histologic healing (based on Geboes Grading System³) at Week M-44 among those without histologic healing at induction baseline.
- Histologic remission based on the Geboes score³ at Week M-44.
- Histologic remission based on the Nancy Histologic Index⁴ at Week M-44.

- Histologic remission based on the Robarts Histopathology Score⁵ (equivalent to histologic remission based on Geboes score) at Week M-44.
- Histologic-endoscopic mucosal healing (Alternative definition 1) at Week M-44.
- Histologic-endoscopic mucosal healing (Alternative definition 2) at Week M-44.
- Deep histologic-endoscopic mucosal healing at Week M-44.
- A combination of symptomatic remission at Week M-44 and histologic-endoscopic mucosal healing at Week M-44 and fecal calprotectin concentration ≤ 250 mg/kg at Week M-44.
- A combination of symptomatic remission at Week M-44 and deep histologic-endoscopic mucosal healing at Week M-44 and fecal calprotectin concentration ≤ 250 mg/kg at Week M-44.
- Change from induction and maintenance baseline in Geboes total score at Week M-44.
- Change from induction and maintenance baseline in Geboes high activity subscore at Week M-44.
- Change from induction and maintenance baseline in Geboes low activity subscore at Week M-44.
- Change from induction and maintenance baseline in Robarts Histopathology Index at Week M-44.
- Change from induction and maintenance baseline in Nancy Histological Index at Week M-44.
- Change from induction baseline in the modified Mayo score at Week M-44.
- Change from maintenance baseline in the modified Mayo score at Week M-44.
- Change from induction baseline in the partial Mayo score at each visit through Week M-44.
- Change from maintenance baseline in the partial Mayo score at each visit through Week M-44.
- Partial Mayo response at each visit through Week M-44.
- Time to first loss of partial Mayo response through Week M-44 among the participants who had achieved partial Mayo response at maintenance baseline.
- Time to first loss of symptomatic remission through Week M-44 among the participants who had achieved symptomatic remission at maintenance baseline.
- Change from induction baseline in the stool frequency and rectal bleeding subscores at each visit through Week M-44.
- Change from maintenance baseline in the stool frequency and rectal bleeding subscores at each visit through Week M-44.
- Change from induction baseline in the full Mayo score at Week M-44.

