5.5.3. Analysis Methods for the Estimands for the Other Endpoints

Unless otherwise specified, other efficacy endpoints listed and defined in Section 5.5. above will be analyzed based on **Randomized Full Analysis Set** according to randomized treatment group regardless of the treatment actually received.

All statistical testing will be performed at the 2-sided 0.05 significance level. No adjustments for multiple comparisons will be made for these other endpoints and nominal p-values will be presented.

Binary Endpoints

The intercurrent events captured for binary endpoints specified in Section 5.3.2. will be applied to each of the above binary endpoints except extraintestinal manifestations. Participants with ICEs in categories 1-4 and 6 will be considered not to have achieved the binary endpoints. For participants experiencing an ICE 5, their observed values (if available) will be used. Note that the application of ICE categories 1-3 overrides that of ICE 5.

Participants with any missing data for an endpoint after application of ICE strategies will be imputed as not achieving the associated binary endpoints. Binary endpoints will be summarized with the number and frequency of participants who achieve the endpoint by treatment group, as well as the associated 95% confidence interval. Treatment comparisons (each guselkumab group versus placebo) will be performed using CMH test stratified by clinical remission status at maintenance baseline and induction dose treatment to compare the proportion of participants achieving the endpoints. In case of rare events, the Fisher's exact test will be used for treatment comparisons.

Continuous Endpoints

The ICEs specified in Section 5.3.2. will be applied to each of the above continuous endpoints, i.e., if a participant has an ICE in categories 1-4 and 6, induction baseline values will be assigned from the point of ICE onward (i.e., no change from baseline). For participants experiencing an ICE 5, their observed values (if available) will be used. Note that the application of ICE categories 1-3 overrides that of ICE 5.

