To account for the missing data (after applying the ICE strategies) for continuous endpoints of change from baseline measured at more than one post-baseline visit through Week M-44, a Mixed-Effect Model Repeated Measures (MMRM) will be used, under the assumption of missing at random (MAR), to test the difference between each guselkumab group and placebo. In MMRM, missing data will not be imputed, but rather missing data will be accounted for through correlation of repeated measures in the model. Additionally, if the MMRM normality assumption is in question, an appropriate transformation may be implemented before fitting the MMRM model.

The explanatory variables of the MMRM model will include treatment group, clinical remission status at maintenance baseline (Yes/No), and induction dose treatment (guselkumab 400 mg, guselkumab 200 mg, placebo crossover to guselkumab 200 mg), respective baseline score, and an interaction term of visit with treatment group.

An unstructured covariance matrix for repeated measures within a participant will be used. The F-test will use Kenward-Roger's approximation for degree of freedom. In case of lack of convergence, empirical structured covariances will be used in the following order until convergence is reached: 1) Toeplitz 2) first order Autoregressive Moving Average.

The treatment difference between each guselkumab group and placebo will be estimated by the difference in the least squares means (LSmeans). The 95% 2-sided CI for the differences in LSmeans and p-values will be calculated based on the MMRM.

Endpoints that are measured at only one post-baseline visit through Week M-44 (e.g., the full Mayo score or modified Mayo score) will be compared between each guselkumab group and placebo using an analysis of covariance (ANCOVA) with treatment group, clinical remission status at maintenance baseline (Yes/No), induction dose treatment, and corresponding baseline value as covariates.

For analyses using ANCOVA, unless otherwise specified, multiple imputation (same as defined in Section 5.3.2.2.2.) will be used for missing data (after applying ICE strategies), under the assumption that the data are missing at random. The analysis will impute the missing scores at Week M-44 using the corresponding value at baseline and related component score at pre-Week M-44 visits if applicable, clinical remission status at maintenance baseline, induction dose treatment, and treatment group.

Ordinal Endpoints

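### Each continuous maintenance outcome is analysed as two change scores that adjust for different baselines, so one randomised contrast gets two answers; carrying both baselines in every model would reconcile them.

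*SAP*

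**What the plan says.** SAP 5.5 lists most continuous outcomes twice. For the partial Mayo score the entries are "Change from induction baseline in the partial Mayo score at each visit through Week M-44" and "Change from maintenance baseline in the partial Mayo score at each visit through Week M-44". The same pairing appears for the modified and full Mayo scores, stool frequency and rectal bleeding subscores, UCEIS, the histology scores, CRP, calprotectin, IBDQ, PROMIS and WPAI-GH.

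SAP 5.5.3 sets the models. For repeated measures, "The explanatory variables of the MMRM model will include treatment group, clinical remission status at maintenance baseline (Yes/No"), then induction dose, then "respective baseline score, and an interaction term of visit with treatment group". For outcomes with one post-baseline visit, the ANCOVA has treatment and remission status at maintenance baseline, with "induction dose treatment, and corresponding baseline value as covariates". On the natural reading, each model carries one value of the outcome: Week I-0 for change from induction baseline, Week M-0 for change from maintenance baseline.

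Two further rules matter:
- After intercurrent events in categories 1-4 and 6, "induction baseline values will be assigned from the point of ICE onward (i.e., no change from baseline").
- The Week M-0 value exists by design. SAP 5.1.4 says "The maintenance baseline is defined as the closest non-missing value on or prior to the maintenance reference start date", and footnote h to Protocol Table 2 carries forward the induction visit: "For all assessments not marked at this visit, data from the study assessments performed at the Week I 12 visit" (or Week I-24).

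**The concern.** Re-randomisation happens at Week M-0, after every randomised participant has responded to induction. For a participant with a given Week M-44 value, the two change scores differ only by the Week M-0 value minus the Week I-0 value, which is fixed before re-randomisation. Both versions therefore target the same between-arm difference, yet they will report different estimates and p-values for it, at each visit and for each outcome.

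Each version also leaves out something prognostic. The induction version lacks the outcome's own value at re-randomisation, apart from what the yes/no remission factor conveys. The maintenance version lacks the Week I-0 value, which the intercurrent-event rule writes directly into the outcome. What is at stake is consistency of reporting and some precision.

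**Working it through.** **Plan figures.** The documents give no SD, correlation or power for continuous endpoints, so no plan figure can be reproduced for this point. The binary sample size, which supplies the arm size used below, does reproduce. For 25% versus 45%, n = [1.960·√(2·0.35·0.65) + 1.282·√(0.25·0.75 + 0.45·0.55)]² / 0.20² = (1.322 + 0.845)² / 0.04 = 117.4, so 118 per group. Power is 90.1% at 118 (stated 90%) and 96.7% at 161 (stated 97%).

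**Why two covariates reconcile the versions.** Let I, M and Y be the Week I-0, Week M-0 and outcome values.

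- Y − I = (Y − M) + (M − I).
- If I and M are both in the model, M − I is an exact linear function of covariates. Moving from one version to the other changes only the coefficients of I and M, and the treatment coefficient is unchanged.
- The same holds in the MMRM, because M − I is the same at every visit.
- If only I or only M is in the model, M − I is not absorbed and the treatment estimates differ.

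This needs the same participants and the same Y in both versions. That follows if the induction value is assigned after an event in both, as the SAP text says, although its no-change gloss fits only the induction version.

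**Precision by formula, without intercurrent events or the remission factor.** With r1 = corr(I,Y) = 0.2, ρ = corr(I,M) = 0.3 and r2 = corr(M,Y), all assumed, R² = (r1² + r2² − 2·r1·r2·ρ)/(1 − ρ²). For r2 = 0.5, R² = (0.04 + 0.25 − 0.06)/0.91 = 0.253. Residual variance relative to I alone is (1 − 0.253)/(1 − 0.04) = 0.778, an SE ratio of 1/√0.778 = 1.13. For r2 = 0.3, 0.4 and 0.6 the variance ratios are 0.934, 0.868 and 0.666.

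**Adding the remission factor.** Over corr(M,Y) 0.2 to 0.6, corr(I,Y) 0.1 to 0.3 and corr(I,M) 0.2 to 0.5, the SE of the planned induction model relative to the two-baseline model is 1.00 to 1.30 (1.297² − 1 = 68% more participants at the extreme). At corr(M,Y) = 0.5 it is 1.06 to 1.11 if remission tracks the score closely and 1.10 to 1.17 if weakly.

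**Adding the intercurrent-event rule.** This used 1,500 simulated trials per row with 161 per arm, a single-visit ANCOVA, corr(I,M) = 0.3, corr(I,Y) = 0.2, I centred 2 SD worse than M and Y, and a true effect of 0.3 SD. One third were in remission at Week M-0 (SAP sample-size assumption: about 33%). Y was set to I after an event. Event rates are assumptions. As a guide, SAP Table 3 assumes Week M-44 clinical response of 51% on placebo and 77% on guselkumab. Since these events count as non-response, that implies ceilings of 49% and 23%.

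| Events, placebo/guselkumab | Remission link | corr(M,Y) | SE, I only | SE, M only | SE, both | Mean gap | I only ÷ both | M only ÷ both |
|---|---|---|---|---|---|---|---|---|
| 0/0 | close | 0.3 | 0.108 | 0.107 | 0.106 | 0.022 | 1.022 | 1.006 |
| 0/0 | close | 0.5 | 0.104 | 0.097 | 0.097 | 0.031 | 1.067 | 0.999 |
| 0/0 | weak | 0.3 | 0.111 | 0.108 | 0.107 | 0.028 | 1.033 | 1.009 |
| 0/0 | weak | 0.5 | 0.113 | 0.100 | 0.100 | 0.043 | 1.132 | 1.001 |
| 30/10% | close | 0.3 | 0.137 | 0.140 | 0.136 | 0.031 | 1.003 | 1.031 |
| 30/10% | close | 0.5 | 0.133 | 0.132 | 0.129 | 0.036 | 1.029 | 1.016 |
| 30/10% | weak | 0.3 | 0.136 | 0.140 | 0.136 | 0.036 | 1.004 | 1.035 |
| 30/10% | weak | 0.5 | 0.138 | 0.133 | 0.131 | 0.043 | 1.051 | 1.015 |
| 50/25% | close | 0.3 | 0.150 | 0.156 | 0.150 | 0.042 | 1.000 | 1.045 |
| 50/25% | close | 0.5 | 0.144 | 0.148 | 0.142 | 0.044 | 1.015 | 1.045 |
| 50/25% | weak | 0.3 | 0.146 | 0.153 | 0.145 | 0.045 | 1.005 | 1.055 |
| 50/25% | weak | 0.5 | 0.146 | 0.148 | 0.142 | 0.048 | 1.028 | 1.047 |

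SEs and gaps are in SD units. With both baselines in each model, the largest difference between versions in any trial was about 7 × 10⁻¹⁵, which is rounding error. With events, the induction-only model loses 0 to 5% in SE (at most 1.051² − 1 = 10.5% more participants) and the maintenance-only model about 2 to 6%. The maintenance-only model is the less precise in six of the eight rows.

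**The case against.** The strongest case against has five parts.

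- **Disease state at re-randomisation is already adjusted for.** A reader might infer that the change-from-induction models ignore it. They do not: remission status at maintenance baseline and induction dose are in every model. This stands, though a yes/no Mayo-based factor probably says little about CRP, calprotectin or patient-reported scores.
- **The precision loss is small.** A reader who applied the two-predictor formula alone, with corr(M,Y) of 0.4 to 0.6, might infer a loss worth 15 to 50% more participants (1/0.868 and 1/0.666). That leaves out the remission factor and the SAP's intercurrent-event rule, and no correlation comes from the documents. With the rule applied the loss is far smaller and is not confined to the induction version.
- **The protocol implies a preference.** Protocol 9.4.1.3 lists the continuous change endpoints from maintenance baseline only, and the induction versions are SAP additions. This stands, but the SAP tests both versions and does not say which one leads.
- **The two versions describe different within-arm changes.** That is true, and it is a reason to present both summaries. It gives no reason for the between-arm contrast to differ. For percentage changes in CRP and calprotectin the contrasts do differ, and a second covariate does not reconcile them.
- **A missing Week M-0 covariate has no rule.** Correct. The MMRM does not impute, and the ANCOVA imputation covers Week M-44 scores only. This adds a small cost to the fix.

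**Conclusion.** The point holds as a matter of consistency, with a modest efficiency element. That the planned versions use different covariates, and that including both baselines makes them agree, follows from the SAP text and algebra. The sizes rest on assumed correlations and event rates: an average gap of about 0.02 to 0.05 SD against an SE of about 0.10 to 0.16 SD, and a gain in SE of about 0 to 30% without intercurrent events or about 0 to 6% with the SAP's rule.

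A reader might infer bias from chance imbalance at Week M-0. The documents do not support that: randomisation keeps both estimates valid. Nor is any confirmatory result at risk. These are other endpoints with nominal p-values under SAP 5.5.3, and no primary or major secondary endpoint, significance level or sample size is affected. This is a worthwhile refinement and not a defect that threatens the trial's conclusions.

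**What to change.** In SAP 5.5.3, include both the induction-baseline and the maintenance-baseline value of the outcome in every maintenance MMRM and ANCOVA of a change score, in both versions. Keep remission status and induction dose as planned. Use one common imputation model for the two ANCOVA versions; otherwise a missing Week M-44 score could be imputed differently in each and the contrasts would separate again. State that the induction value is assigned after intercurrent events in both versions, and that percentage-change endpoints are outside this provision.

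Add a rule for participants without a Week M-0 value, for example a single imputation of the covariate made without reference to treatment, applied to both versions so that they use the same participants. Few should need it, because SAP 5.1.4 already takes the closest earlier post-induction-baseline value.

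The cost is a short SAP edit, one covariate (one degree of freedom) per model and this rule. No new data are needed. If the sponsor prefers not to change the models, the lesser remedy is to name one change score per outcome as the inferential version and report the other descriptively.

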Assays for fecal calprotectin will be performed by the central laboratory using a validated method. Fecal calprotectin normalization is defined as fecal calprotectin concentration \leq 250 mg/kg.

Patient-Reported Outcomes

IBDQ

The IBDQ¹³ is a validated, 32-item, self-reported questionnaire for participants with IBD that will be used to evaluate the disease-specific HRQoL across 4 dimensional scores: bowel symptoms (loose stools, abdominal pain), systemic functions (fatigue, altered sleep pattern), social function (work attendance, need to cancel social events), and emotional function (anger, depression, irritability). Scores range from 32 to 224, with higher scores indicating better outcomes.

The individual IBDQ dimensions will be calculated when no more than 1 item is missing in the dimension. If an item is missing, it will be estimated using the average value across the non-missing items. If any of the 4 dimensions of the IBDQ cannot be calculated, then the total IBDQ score cannot be calculated and will be missing for that visit.

- **IBDQ remission:** total IBDQ score ≥ 170 (Irvine et al, 1994¹³; Higgins et al, 2005¹⁴)
- **Maintenance of IBDQ remission:** in IBDQ remission at both Week M-28 and Week M-44 among participants with IBDQ remission at the maintenance baseline.

PROMIS-29

The Patient-Reported Outcomes Measurement Information System (PROMIS)-29 is a validated general health profile instrument that is not disease-specific. It is a collection of short forms containing 4 items for each of 7 domains (depression, anxiety, physical function, pain interference, fatigue, sleep disturbance, and ability to participate in social roles and activities). PROMIS-29 also includes an overall average pain intensity 0-10 numeric rating scale. Norm-based scores have been calculated for each domain on the PROMIS measures, with a score of 50 representing the mean or average of the reference population. On symptom-oriented domains of PROMIS-29 (anxiety, depression, fatigue, pain interference, and sleep disturbance), higher scores represent worse symptomatology. On the function-oriented domains (physical functioning and social role), higher scores represent better functioning. Additionally, the physical component summary score (PCS) and mental component summary score (MCS) will each be derived from all 7 domain scores of PROMIS-29 (Hays et al, 2018¹⁷) as measures for general health related quality (HRQOL). Higher PCS and MCS scores indicate better HRQOL.

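### The MMRM in SAP 5.5.3 fits one baseline slope for all visits; if that slope changes over 44 weeks, the many-visit exploratory contrasts lose a little precision that a baseline-by-visit term would recover

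*SAP*

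**What the plan says.** SAP 5.5.3 (Continuous Endpoints) is the only place that specifies the MMRM; SAP 5.1 and Protocol 9.4.2.3.4 name the method without listing terms. The fixed effects read: "The explanatory variables of the MMRM model will include treatment group, clinical remission status at maintenance baseline (Yes/No), and induction dose treatment", followed by the "respective baseline score, and an interaction term of visit with treatment group". The covariance is free: "An unstructured covariance matrix for repeated measures within a participant will be used". Treatment differences are taken from the LS means.

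The covariate depends on the endpoint. SAP 5.5 lists both "Change from maintenance baseline in the partial Mayo score at each visit through Week M-44" and "Change from induction baseline in the partial Mayo score at each visit through Week M-44", and likewise for the stool frequency and rectal bleeding subscores, absolute stool number, CRP and the patient-reported scores. So the baseline is M-0 in some models and I-0 in others.

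The number of visits also differs. Protocol Table 2 schedules partial Mayo at 11 post-baseline visits (M-4 to M-44), CRP at 6, and IBDQ, PROMIS and fecal calprotectin at 2. SAP 5.5.1 reflects the last case in its definition of maintained IBDQ remission: "in IBDQ remission at both Week M-28 and Week M-44 among participants with IBDQ remission at the maintenance baseline".

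Under SAP 5.5.3, a participant with an intercurrent event in categories 1-4 or 6 has the induction baseline value assigned from then on. SAP 5.3.2 counts dose adjustment, including sham adjustment, as such an event, and SAP 1.3.1 allows it only between M-8 and M-32. All these endpoints are tested without multiplicity adjustment.

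**The concern.** A baseline main effect without a visit interaction forces the regression on baseline to be the same 4 weeks and 44 weeks after M-0. With an unstructured covariance, the fitted slope is a weighted average over visits. If the true slopes fall, it lies above the M-44 slope; if they rise, it lies below. Either way the M-44 contrast is adjusted by an amount that does not fit M-44, and its variance is larger than it need be.

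The SAP's own rule gives a reason to expect movement. At M-4 no value has yet been replaced because of a dose adjustment; by M-44 all such replacements are in place. In models with the I-0 covariate a replaced outcome equals the covariate, which pulls the later slopes up. In models with the M-0 covariate, ordinary loss of correlation over 44 weeks would pull them down.

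The same section analyses single-visit endpoints such as the modified Mayo score by ANCOVA, which does fit a slope specific to M-44. At stake is the precision of some exploratory estimates.

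**Working it through.** **The plan's own figure.** The documents state no SD, correlation or precision for any MMRM endpoint. The one related figure is power for the binary primary endpoint (25% vs 45%, two-sided 0.05). With mean rate 0.35:

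(0.20·√118 − 1.960·√(2·0.35·0.65)) / √(0.25·0.75 + 0.45·0.55) = (2.173 − 1.322)/0.660 = 1.29, so power is 0.901 against the stated 90%. With 161 per group it is 0.967 against 97%.

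These reproduce. They do not depend on the MMRM and supply only the group size.

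**Formula.** Take complete data, visit-by-treatment means and unstructured covariance, and leave the other covariates out. Let b be the vector of true baseline slopes by visit and S the residual covariance given baseline. The common slope converges to

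b_c = (1′S⁻¹b)/(1′S⁻¹1),

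and the M-44 variance ratio, common against visit-specific slope, is

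r = 1 + (b₄₄ − b_c)²·var(baseline)/var(Y₄₄ | baseline).

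Modelling change instead of the value subtracts 1 from every slope and from b_c, so r is the same.

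**Linear patterns, 11 visits** (assumed: unit variances, so slope equals correlation; residual correlation 0.9 per visit step):

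| Baseline correlation, M-4 to M-44 | b_c | r at M-44 |
|---|---|---|
| constant | same slope | 1.00 |
| 0.5 to 0.35 | 0.433 | 1 + 0.083²/0.878 = 1.008 |
| 0.4 to 0.2 | 0.309 | 1 + 0.109²/0.960 = 1.012 |
| 0.6 to 0.3 | 0.487 | 1 + 0.187²/0.910 = 1.038 |
| 0.6 to 0.2 | 0.457 | 1 + 0.257²/0.960 = 1.069 |
| 0.7 to 0.3 | 0.581 | 1 + 0.281²/0.910 = 1.087 |

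Simulation of the last three patterns (4,000 trials each, 161 per arm) gave 1.03, 1.05 and 1.07, slightly lower. Averaged over the 11 visits, the closed-form ratios for those three are only 1.012, 1.022 and 1.028.

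**Curved patterns.** With a stable component plus a decaying one (half-life 16 weeks), 0.65 to 0.44 gives 1.016 and 0.72 to 0.37 gives 1.05; six visits give nearly the same. Steeper cases go further: 0.79 to 0.30 gives 1.12, and pure AR(1) decay from 0.84 to 0.15 gives 1.28. In those two the common-slope contrast is less precise than one with no baseline adjustment (whose ratios are 1.10 and 1.02).

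**Two visits (M-28, M-44).** Over the same family, r is at most 1.006.

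**With the intercurrent-event rule** (200,000 simulated participants; assumed event rates about 58% placebo and 22% guselkumab by M-44; the I-0 value itself assigned after an event):

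| Natural pattern | Covariate | Slope, M-4 to M-44 | b_c | r at M-44, 11 visits |
|---|---|---|---|---|
| fading | M-0 | 0.72 to 0.44 | 0.67 | 1.029 |
| fading | I-0 | 0.27 to 0.52 | 0.34 | 1.013 |
| no fade | M-0 | 0.60 to 0.62 | 0.61 | 1.000 |
| no fade | I-0 | 0.22 to 0.59 | 0.31 | 1.030 |

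Two-visit ratios in these runs are at most 1.001. Applying the same rule to the three steeper linear patterns, with event rates of 40-57% placebo and 14-21% guselkumab, gives 1.015 to 1.043 for M-0 and 1.003 to 1.014 for I-0.

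**Translation.** SE rises by √r − 1: 1.5% at r = 1.03 and 4.4% at r = 1.09. A contrast with 90% power under visit-specific slopes has power Φ(3.242/√r − 1.960), which is 89.1% at 1.03 and 87.4% at 1.09. In participants, 161·(1 − 1/r) is about 5 and 13 per group.

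**The case against.** The strongest reply is that the loss is hypothetical. No correlation appears in either document, and with constant slopes nothing is lost. That stands, and it is why the size is given as a range under stated assumptions. A reader might infer that the influence of the M-0 value is known to fade and that the M-44 contrast therefore uses the wrong slope. The documents do not support that. Many endpoints use I-0, where the replacement rule can make the slope rise; with M-0 and no natural fading, the rule alone leaves the slope almost flat (0.60 to 0.62).

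Nor should M-44 be treated as the sole time point. Partial Mayo, its subscores and absolute stool number are listed at each visit, and the average loss over visits is smaller than at M-44.

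A reader might also infer bias. With complete data and randomized groups there is none from this source; over-adjustment acts only on chance imbalance. Under missing-at-random dropout a wrong mean model could add some, which was not quantified.

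It is also fair to say that the list of terms is not strictly closed: it omits the visit main effect as well, which the model plainly needs. That weakens a literal reading, but it also means that two programmers could fit different models. Finally, remission status at M-0 could be given a visit interaction by the same logic. Which covariates to interact is partly preference; the quantitative baseline score is the usual first choice.

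**Conclusion.** The point holds as a minor, free improvement. As written, SAP 5.5.3 fits a single slope on the respective baseline. A change in that relation over 44 weeks is likely, most clearly for I-0 endpoints as replacements accumulate, and it would cost some precision in the visit-specific contrasts.

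Under the assumed patterns, the M-44 variance for many-visit endpoints is about 0 to 9% higher before the intercurrent-event rule; only decay steeper than these linear patterns goes beyond that. With the rule applied it is about 1 to 3% higher where the slope moves at all, and 4% in the steepest pattern with fewer events. Endpoints measured only at M-28 and M-44 gain practically nothing. The size rests on assumed correlations, event rates and, before the rule, complete data.

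No confirmatory conclusion is affected. The primary and major secondary endpoints are binary and use CMH tests, and the full and modified Mayo scores use ANCOVA at M-44.

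**What to change.** In SAP 5.5.3, specify the MMRM fixed effects in full: treatment, visit, treatment-by-visit, respective baseline score, baseline-by-visit, clinical remission status at maintenance baseline, and induction dose treatment. This also settles the unlisted visit main effect.

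The cost is one sentence in the SAP and one extra parameter per post-baseline visit beyond the first: 10, 5 or 1 for endpoints with 11, 6 or 2 visits. That is negligible with about 484 participants, or up to 484 × 11 = 5,324 observations for an 11-visit endpoint. No new data are needed, and if the slopes prove constant essentially nothing is lost. The change should be made before the Week M-44 unblinding.
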